6.1 Sample Size Determination

We propose a two-period two-treatment cross-over study, where each participant gets NAC infusion and saline infusion, in randomized order as shown in Figure under 2.1. Our primary outcome is the peak epinephrine response during the third hypoglycemic clamp of each infusion experiment, thus each participant will have two observations: one epinephrine response from their NAC infusion experiment and one epinephrine response from their saline infusion experiment. We expect to recruit 18 individuals in order to complete 15 studies. Additional participants will be recruited if needed to have 15 completed studies. If NAC prevents HAAF, then the epinephrine response during the third hypoglycemic clamp after NAC infusion will still be high, while the epinephrine response during the third hypoglycemic clamp after saline infusion will be blunted. Therefore ***this within-person difference in epinephrine response will be large and positive***. Assuming a one-sided type I error of 5% and a power of 85%, we can detect an epinephrine response difference between NAC and saline of at least 154 units. This magnitude of difference is comparable to the difference between healthy controls and subjects with T1DM and hypoglycemia unawareness that we found in a previous study. In that study, participants underwent a hyperinsulinemic hypoglycemic clamp and the epinephrine response during hypoglycemia in the subjects with T1DM was 121 ± 168 pg/ml vs. 278 ± 134 pg/ml in controls.

6.2 Statistical Methods

Our primary outcome is the peak epinephrine response during the third hypoglycemic clamp of each infusion experiment, thus each participant will have two observations: one from their NAC infusion experiment and one from their saline infusion experiment. We will fit a general linear mixed model with fixed effects for treatment (NAC vs. saline), treatment order (NAC first vs. saline first), and period (Part 1 vs. Part 2) and a random effect for participant. We are confident that our study design, with a washout period of 8 weeks between Parts 1 and 2, has minimized the possibility of a treatment effect from Part 1 that lingers into Part 2. We will also consider adjustment for important baseline characteristics, such as age, gender, and duration of diabetes. Diagnostics will be examined to assess model assumptions. Secondary outcomes include: the within-person difference in peak epinephrine response between the first hypoglycemic clamp (when an infusion is given) and the third hypoglycemic clamp (when no infusion is given) of each infusion experiment; symptom scores during the third hypoglycemic clamp of each infusion experiment; and the within-person difference in symptom scores between the first hypoglycemic clamp and the third hypoglycemic clamp of each infusion experiment.

CONFIDENTIAL

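### If the participant random effect in 6.2 is fitted by REML with its variance bounded at zero, the one-sided 5% test runs at about 5.6–5.9% when the within-person correlation is near zero; an unstructured 2×2 covariance holds 5%

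*Combined protocol and SAP*

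**What the plan says.** Section 6.1 describes the design: "We propose a two-period two-treatment cross-over study". The primary outcome is peak epinephrine in the third clamp, so each person contributes one value under NAC and one under saline. The sizing statement begins "Assuming a one-sided type I error of 5% and a power of 85" percent, and continues "we can detect an epinephrine response difference between NAC and saline of at least 154 units". The number of completers comes from "We expect to recruit 18 individuals in order to complete 15 studies". The only SDs given are from a previous study in two separate groups, where the response in participants with type 1 diabetes "was 121 ± 168 pg/ml vs. 278 ± 134 pg/ml in controls". No within-person correlation and no SD of the within-person difference is stated.

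Section 6.2 plans a linear mixed model. Treatment and the order of the two infusions enter as fixed effects, and the rest of the model is given by the words "and period (Part 1 vs. Part 2) and a random effect for participant". The Statistical Methodology entry of the Study Summary repeats it. Neither place says whether the fit is REML or ML, whether the participant variance may go below zero, how degrees of freedom are obtained, or whether the test is one-sided. One-sidedness appears only in 6.1.

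**The concern.** With two observations per person, a participant random intercept makes the within-person covariance equal to the participant variance. If software holds that variance at or above zero, a negative sample covariance is replaced by zero and the error variance of the treatment contrast is re-estimated by pooling within-person and between-person variation. Pooling happens only when it gives the smaller error variance. A rule that always takes the smaller of two estimates makes the test anti-conservative when the true correlation is near zero or negative.

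At stake is the 5% one-sided level that 6.1 promises, and the width of the matching confidence limit. The choice matters more with 15 pairs than it would in a large trial. The point estimate is not at stake: for complete pairs it is the same under every covariance considered here.

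**Working it through.** **Inputs from the documents.** 15 completers, one-sided 5%, 85% power, difference 154, SDs 168 and 134 (6.1); fixed effects for treatment, order and period (6.2). **Assumed:** the within-person correlation r, shown over a range; zero-bounded REML; 8 and 7 completers in the two orders.

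**Step 1. Reproduce the 154.** At r = 0:

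- SD of the difference = √(168² + 134²) = √46,180 = 214.9. Standard error = 214.9/√15 = 55.5.
- Normal calculation: (1.645 + 1.036) × 55.5 = 149.
- Noncentral t: about 157 on 14 or 13 df. Power at 154 is about 84%.

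The stated 154 lies between these results. An exact match needs r of about 0.03–0.04 (t) or −0.07 (normal). Zero is therefore a fair reading, but it depends on using the two cited SDs, one per treatment. On the t calculation, 154 corresponds to an SD of the difference of about 214.9 × 154/156.6 = 211. With 168 under both treatments, r = 1 − 211²/(2 × 168²) = 0.21. With 134 under both, r = 1 − 211²/(2 × 134²) = −0.24.

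**Step 2. What the bounded fit does.** For each person let d be the NAC-minus-saline difference and s the sum of the two values. Pool their variances within order group on 13 df and call them V_d and V_s. Then V_s − V_d is four times the sample within-person covariance.

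- Covariance zero or positive: the fit uses V_d, which is the period-adjusted paired analysis.
- Covariance negative: the participant variance is set to 0 and the fit uses (V_d + V_s)/2, which is smaller than V_d.

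So the error variance used is min{V_d, (V_d + V_s)/2}. At r = 0 the two cases are equally likely.

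**Step 3. Type I error.** Simulation under no treatment effect, nominal one-sided 5%:

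| r | Bound hit | 13 df | Satterthwaite df |
|---|---|---|---|
| −0.3 | 86% | 6.9% | 7.5% |
| −0.2 | 76% | 6.3% | 6.8% |
| −0.1 | 64% | 5.9% | 6.3% |
| 0 | 50% | 5.6% | 5.9% |
| 0.2 | 24% | 5.2% | 5.3% |
| 0.3 | 14% | 5.1% | 5.1% |
| 0.5 | 3% | 5.0% | 5.0% |

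The period-adjusted paired test on 13 df gives 5.0% in every row. Using SDs of 168 and 134 in place of equal SDs leaves the r = 0 row unchanged. With 18 completers split 9 and 9 the r = 0 figures are 5.6% and 5.8%.

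**Step 4. Where the excess arises.** At r = 0, trials that hit the bound reject in 4.4% (13 df) to 5.0% (Satterthwaite) of cases, and their error variance is right on average. The other trials reject in 6.8%, and there the bounded model and the paired test are identical. The paired test reaches 5.0% overall because it rejects in only about 3.2% of the bound-hit trials, which offsets the 6.8%. Pooling removes that offset.

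**Step 5. Power at 154, r = 0, SDs 168 and 134.** Paired analysis 83.6%; bounded random intercept 86–87%. The gap reflects a test running above 5%.

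**The case against.** Several points on the other side stand.

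- **The correlation is not stated.** Section 6.1 cites the two SDs to show that 154 is comparable with an earlier group difference, and does not say that they were inputs. They come from two populations, while 6.3 now restricts the trial to healthy volunteers. The same person repeats the same procedure about 8 weeks later, so a positive correlation is plausible, and at r of 0.3 or more the excess is negligible.
- **The fit is not stated.** A fit that allows negative covariance holds 5.0%. A reader might infer that the planned model itself runs at 5.6–5.9%. The documents support only that it would do so under zero-bounded REML at r = 0.
- **Zero correlation is not excluded.** A reader might infer that a random intercept cannot represent r = 0. It can, with a participant variance of 0; only negative correlation is ruled out.
- **The bound-hit trials are not the faulty ones.** A reader might infer that the standard error is too small in those trials. Step 4 shows otherwise at r = 0; the excess belongs to the smaller-of-two rule taken as a whole.
- **Normal-based tests are a separate matter.** A z test gives 6.9% at r = 0 but still 6.2% at r = 0.5, where the bound hardly matters. Most of that excess comes from using z in place of t on 13 df.

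A participant random effect is also a standard cross-over model, and this is a proof-of-principle study. These points keep the matter small. They do not remove it, because 6.2 does not say which fit will be used, and some of the fits it permits miss the level set in 6.1.

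**Conclusion.** The point holds in a limited, conditional form. If 6.2 is carried out by zero-bounded REML and the true within-person correlation is near zero, the one-sided 5% test runs at about 5.6–5.9%, an excess of 0.6–0.9 percentage points. The excess grows if the correlation is negative (6.3–6.8% at r = −0.2), is about 0.1 point at r = 0.3 and is absent at r = 0.5. Both conditions are assumptions: the bounded fit is common but not stated, and r near 0 is inferred from a sample size that it reproduces only approximately. Estimates are unaffected, and a clear result would not be overturned. It is a minor improvement worth making because the remedy is exact and nearly free.

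**What to change.** In 6.2, and in the matching Study Summary entry, keep treatment, order and period as fixed effects. Replace the participant random effect with an unstructured 2×2 within-participant covariance, fitted by REML with Kenward-Roger degrees of freedom, and state that the treatment test is one-sided at 5%. For complete pairs this is the period-adjusted paired t-test on 13 df with 15 completers. It gives the same estimate, and it agrees with the random-intercept REML fit on 13 df whenever the estimated correlation is positive.

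The cost is one sentence. If the correlation is near 0, power at 154 is about 84% instead of an apparent 86–87%. At moderate positive correlation the results are essentially the same.

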1.3 Preclinical Data

In animal models, administration of N-acetyl cysteine (NAC) during episodes of hypoglycemia prevents the development of HAAF, possibly by preventing the hypoglycemia induced rise in hypothalamic reactive oxygen species known to occur during acute episodes of hypoglycemia .

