2.2 Primary Study Endpoints

Primary endpoint will be the within person difference in epinephrine secretion during the morning episodes of hypoglycemia on days one and two under the two treatment conditions. Epinephrine secretion during hypoglycemia is assessed by collecting blood samples for measurement of epinephrine concentrations at baseline and every 15 minutes during the period of hypoglycemia (starting at point where blood glucose is first ≤ 55 mg/dl) in the clamp studies done in the mornings of days 1 and 2 of both parts 1 and 2.

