Subjects will be asked to report to the research center by 7 am on the first day of the study after fasting overnight. On arrival, intravenous lines will be placed in each arm (one will be used for infusions and the other for blood sampling). A minimum of 30 minutes after the IVs are placed, baseline blood samples will be drawn for glucose, epinephrine, norepinephrine, cortisol, cysteine and glutathione measurements. Subjects will then be given diphenhydramine 25 mg IV push immediately prior to the start of a 60 minute infusion of NAC (150 mg) or a similar volume of saline between 8 am and 9 am, followed by a four hour infusion of 50 mg of NAC. Thirty minutes after the start of the NAC infusion, a hyperinsulinemic (2.0 $\mu\text{u/kg/min}$) hypoglycemic (target = 50 mg/dl) clamp protocol will be started. During the morning study, blood samples will be collected every 5 minutes for monitoring of blood glucose levels and every 15 minutes for later measurement of serum epinephrine, norepinephrine, cortisol. Plasma and red blood cells samples will also be collected every 15 minutes for later measurement of NAC, cysteine, glutathione, and GSH/GSSG ratios (redox status). During the final 15 minutes of the morning clamp, subjects will be asked to quantitate their symptoms using a standardized method (13). At the completion of the morning clamp, glucose will be given to return the participant to euglycemia. 2 hours after the end of the morning clamp, a second hyperinsulinemic (2.0 $\mu\text{u/kg/min}$) hypoglycemic (target = 50 mg/dl) clamp protocol will be followed over two hours. The afternoon clamp study will proceed as in the morning except that no serum or plasma will be collected except for the monitoring of glucose and collection of samples for subsequent measurement of NAC,

CONFIDENTIAL

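### The change from clamp 1 to clamp 3 is used as an efficacy measure, but clamp 1 runs during the infusion, so an acute NAC effect on day 1 can mimic or hide prevention

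*Combined protocol and SAP*

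**What the plan says.** Section 6.2 compares peak epinephrine "between the first hypoglycemic clamp (when an infusion is given) and the third hypoglycemic clamp (when no infusion is given) of each infusion experiment", and lists for symptoms the "within-person difference in symptom scores between the first hypoglycemic clamp and the third hypoglycemic clamp of each infusion experiment". Both are secondary outcomes there. The primary in sections 6.1 and 6.2 does not use clamp 1: "Our primary outcome is the peak epinephrine response during the third hypoglycemic clamp of each infusion experiment".

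Section 2.2 (also the Study Summary and the Primary Objective) defines the primary endpoint as the "within person difference in epinephrine secretion during the morning episodes of hypoglycemia on days one and two under the two treatment conditions". Section 2.3 does the same for symptom scores.

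On timing, section 5 (Study Procedures) states: "Subjects will then be given diphenhydramine 25 mg IV push immediately prior to the start of a 60 minute infusion", and then "Thirty minutes after the start of the NAC infusion, a hyperinsulinemic" clamp begins. The Study Summary gives a 5-hour infusion on day 1. Clamp 3, on the morning of day 2, has no infusion and no premedication described.

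On mechanism, section 1.3 reports that in animals NAC given during hypoglycemia prevents HAAF, "possibly by preventing the hypoglycemia induced rise in hypothalamic reactive oxygen species known to occur during acute episodes of hypoglycemia".

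**The concern.** A change from clamp 1 to clamp 3 measures protection against blunting only if clamp 1 shows the response before treatment could alter it. Here clamp 1 is itself a treated measurement. No hypoglycemic clamp precedes the infusion within a part, and the only epinephrine sample taken before drug is drawn before any hypoglycemia.

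If NAC lowers the acute response on day 1, the NAC part shows a smaller fall to day 2 and looks protective even when the two clamp 3 responses are identical. If NAC raises the acute response, real preservation is masked. Section 2.1 asks how day 1 treatment affects day 2 responses. The clamp 3 contrast answers that directly; the change answers it only if NAC has no acute effect at clamp 1. The plan neither argues for that condition nor provides a separate test of it.

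**Working it through.** **1. Is clamp 1 on drug?** Section 5 starts the clamp 0.5 h after the infusion begins. The Study Summary gives a 2 h clamp and a 5 h infusion. The clamp therefore runs from 0.5 h to 2.5 h, wholly inside the infusion. The visit table gives 8-10 AM, but also describes this clamp as done with the infusion.

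**2. What does the change contrast estimate?** Write C1 and C3 for the clamp 1 and clamp 3 responses, N for NAC and S for saline.

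- P = C3(N) − C3(S), the prevention effect.
- A = C1(N) − C1(S), the acute effect.
- Contrast in change = [C3(N) − C1(N)] − [C3(S) − C1(S)] = P − A.

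This equals P only if A = 0. A premedication effect d that adds equally to C1(N) and C1(S) drops out of A, and so out of P − A. It stays in each within-part change.

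**3. The plan's own figure.** Section 6.1 gives a detectable difference of 154 units with 15 completers, one-sided 5% error and 85% power. The SD of the paired difference is not stated. Assuming zero within-person correlation and the two SDs in section 6.1:

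- SD = √(168² + 134²) = √46180 = 214.9.
- Normal approximation: (1.645 + 1.036) × 214.9 / √15 = 148.8.
- Noncentral t, 14 df: 156.6.

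The stated 154 lies between these, so 214.9 is a reasonable working SD. This figure concerns the clamp 3 contrast, and nothing here requires it to change.

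**4. Size of the shift (A is assumed).** Take 278 pg/ml, the control mean in section 6.1, as the day 1 level, with P = 0 and A = −p × 278:

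| p | Shift in change contrast |
|---|---|
| 0.10 | 0.10 × 278 = 28 pg/ml |
| 0.20 | 0.20 × 278 = 56 pg/ml |
| 0.30 | 0.30 × 278 = 83 pg/ml |

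An acute rise of the same size shifts the contrast by the same amount the other way.

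**5. What this could do to a test of the change.** Illustration: one-sided paired t at 5%, n = 15, period effects ignored. The NAC minus saline difference has SD 214.9 at each clamp. With correlation c between the clamp 1 and clamp 3 differences, the SD of the change contrast is 214.9 × √(2(1 − c)).

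| P | A | P − A | Rejection rate, change (c = 0 / 0.5 / 0.8) | Rejection rate, clamp 3 alone |
|---|---|---|---|---|
| 0 | 0 | 0 | 5% / 5% / 5% | 5% |
| 0 | −50 | 50 | 15% / 22% / 39% | 5% |
| 0 | −77 | 77 | 24% / 37% / 67% | 5% |
| 154 | 0 | 154 | 59% / 84% / 99% | 84% |
| 154 | +77 | 77 | 24% / 37% / 67% | 84% |

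The values of A (77 is half of 154) and of c are assumptions. The identity in step 2 is not.

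**The case against.** The strongest reply is that the plan already rests on the right quantity. Sections 6.1 and 6.2 make clamp 3 epinephrine primary, section 6.2 lists clamp 3 symptom scores as a secondary outcome, and the sample size and hypothesis use clamp 3 only. This stands. A reader might infer that the primary analysis is biased; as modelled in section 6.2 it is not.

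Section 2.2 could also be read as NAC minus saline on each day, which would already include the clamp 1 contrast. That reading is possible but less natural, and section 6.2 lists no clamp 1 contrast. The wording needs to be settled either way.

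The plan never calls clamp 1 a pre-treatment baseline, and never says that a change contrast alone will be taken as prevention. True, but it lists the change among the efficacy outcomes without a caveat.

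A reader might infer from section 1.3 that NAC is known to alter the acute epinephrine or symptom response. The section does not say so: it offers a possible hypothalamic mechanism in animals. Nor can A = 0 be taken for granted. Section 1.5 reports anaphylactoid reactions in 10 + 16 + 2 = 28 of 180 recipients, all within 2 hours of administration. That window overlaps clamp 1, and only participants whose infusion is stopped are withdrawn. Whether milder reactions would move the scores is unknown.

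A reader might also blame diphenhydramine for a false NAC versus saline difference. It precedes both infusions, so an additive effect cancels. Only an interaction with NAC would leave a bias, and the documents suggest none.

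**Conclusion.** The concern holds as one of interpretation. The change contrast equals the clamp 3 contrast minus the clamp 1 contrast, and the plan does not examine the second term separately. That follows from the design and needs no assumption.

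The size is unknown. The 28-83 pg/ml range rests on an assumed 10-30% acute effect and on a control mean borrowed from another study. It should not be read as an estimated bias, nor as a share of the 154-unit target, which belongs to the unaffected clamp 3 analysis.

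The reach is two secondary outcomes in section 6.2, plus the endpoints in sections 2.2 and 2.3 on their natural reading. The headline result is exposed only if section 2.2, rather than section 6.2, ends up defining the primary endpoint.

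The within-part change has further limits as a measure of blunting. Premedication preceded clamp 1 only, and section 5 gives clamp 1 a 50 mg/dl target but steps clamp 3 through 75, 65, 55 and 45 mg/dl. This is a cheap improvement.

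**What to change.** 1. Align sections 2.2 and 2.3, with the matching Study Summary and objectives text, with section 6.2, so that the prevention claim rests on the NAC versus saline contrast at clamp 3, for epinephrine and for symptoms.
2. Add to section 6.2 the NAC versus saline contrast at clamp 1 as a separate outcome, labelled the acute effect of NAC, using the same crossover model.
3. Report the change from clamp 1 to clamp 3 as supportive or descriptive, always beside the clamp 1 contrast. Note that clamp 1 alone had infusion and diphenhydramine, and that the two clamps have different glucose targets.

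Using the saline-part clamp 1 as a common reference for both parts is not advised. For the NAC part it comes from the other period, about 8 weeks away, and for those given NAC first it follows NAC and three earlier clamps. That would bring period and possible carryover effects into a within-part measure.

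The cost is some wording and the existing model fitted to clamp 1 data already scheduled for collection. The small downside is that the change score no longer stands alone as evidence of efficacy.

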6.3 Subject Population(s) for Analysis

In this version of the protocol, we intend to only study healthy volunteers. In the original version, we intended to enroll humans with type 1 diabetes of less than 20 years duration, with A1c 6.9-8.2%, who were aware of hypoglycemia but were unable to reach our recruitment goals with this population. More than 45 potential participants were contacted over 14 months and only one subject was able to complete the entire protocol. The reasons potential participants refused enrollment included strong preferences to not experience hypoglycemia and inability to commit the time necessary to complete the study. Previously our group has had no trouble enrolling enough normal volunteers to participate in studies in which they were asked to experience several periods of hypoglycemia. Thus, we believe that we will meet our recruitment goals by changing the population to normal volunteers. In addition, this is a proof of principle study in which the impact of NAC on hypoglycemia induced blunting of the counterregulatory response will be measured. Normal volunteers who participate in this protocol are expected to have the same degree of hypoglycemia induced blunting in their counterregulatory response as patients with type 1 diabetes and normal awareness of hypoglycemia. Therefore, this redesign will allow us to determine if NAC works under controlled conditions. If it does, it will provide rationale to use in in patient populations in the future.

Exclusion criteria will include history of diabetes, hyperglycemia, stroke, seizures, arrhythmias, active cardiac disease, pregnancy or plan to become pregnant during the study period; diagnosis of asthma (increases risk of hypersensitivity reactions to NAC); use of anti-oxidants or drugs that can alter glucose metabolism; concomitant medical problems that may prevent the subject from successfully completing the protocol; and an unwillingness to avoid exercise during the 7 days before each part of the study.

7 Safety and Adverse Events

